**Laboratory Data**

**K. Haematology**

K1. Hgb (g/dl) decrease from pre-treatment	1.0 – 1.4	1.5 – 2.0	2.1 – 2.9, or Hgb < 8.0, > 7.0	≥ 3.0; or Hgb < 7.0
K2. Leukopenia (total WBC) × 1000	3.0 – 3.9	2.0 – 2.9	1.0 – 1.9	< 1.0

**Rheumatology Common Toxicity Criteria v.2.0**

**Based on Woodworth TG, et al. Standardizing assessment of adverse effects in rheumatology clinical trials II. Status of OMERACT Drug Safety Working Group May 2006: OMERACT 8. Standardizing Assessment and Reporting of Adverse Effects in Rheumatology Clinical Trials: Enabling Description of Comparative Safety Profiles for Antirheumatic Therapies**

K3. Neutropenia (× 1000)	1.5 – 1.9	1.0 – 1.4	0.5 – 0.9	< 0.5
K4. Lymphopenia (× 1000)	1.5 – 1.9	1.0 – 1.4	0.5 – 0.9	< 0.5
K5. Platelets (× 1000)	75 – LLN	50 – 74.9	20 – 49.9; platelet transfusion required	< 20; recurrent platelet transfusions
L. Chemistry				
L1. Hypercalcaemia (mg/dl)	1.1 × ULN – 11.5	11.6 – 12.5	12.6 – 13.5; or symptoms present	> 13.5; or associated coma
L2. Hyperglycemia (mg/dl) Fasting	140 – 160	161 – 250	251 – 500	> 500, or associated with ketoacidosis
L3. Hyperkalaemia (mmol/l)***	5.5 – 5.9	6.0 – 6.4	6.5 – 7.0 or any ECG change	> 7.0 or any arrhythmia
L5. Hypocalcaemia (mg/dl)	0.9 × LLN – 7.8	7.7 – 7.0	6.9 – 6.5; or associated with symptoms	< 6.5 or occurrence of tetany
L6. Hypoglycemia (mg/dl)	55 – 64 (no symptoms)	40 – 54 (or symptoms present)	30 – 39 (symptoms impair function)	< 30 or coma
L7. Hyponatraemia (mmol/l)***	-	125 – 129	120 – 124	< 120
L8. Hypokalaemia (mg/dl)***	-	3.0 – 3.4	2.5 – 2.9	< 2.5

**Rheumatology Common Toxicity Criteria v.2.0**

**Based on Woodworth TG, et al. Standardizing assessment of adverse effects in rheumatology clinical trials II. Status of OMERACT Drug Safety Working Group May 2006: OMERACT 8. Standardizing Assessment and Reporting of Adverse Effects in Rheumatology Clinical Trials: Enabling Description of Comparative Safety Profiles for Antirheumatic Therapies**

L9. CPK (also if polymyositis-disease ****)	1.2 – 1.9 × ULN	2.0 – 4.0 × ULN	4.0 × ULN with weakness but without life-threatening signs or symptoms	> 4.0 × ULN with signs or symptoms of rhabdomyolysis or life-threatening
L10. Serum uric acid	1.2 – 1.6 × ULN	1.7 – 2.9 × ULN	3.0 – 5.0 × ULN or gout	NA
L11. Creatinine (mg/dl)****	1.1 – 1.3 × ULN	1.4* – 1.8 × ULN	1.9 – 3.0 × ULN	> 3.0 × ULN
L12. SGOT (AST)	1.2 – 1.5 × ULN	1.6 – 3.0 × ULN	3.1 – 8.0 × ULN	> 8.0 × ULN
L13. SGPT (ALT)	1.2 – 1.5 × ULN	1.6 – 3.0 × ULN	3.0 – 8.0 × ULN	> 8.0 × ULN
L14. Alkaline phosphatase	1.1 – 1.5** × ULN	1.6 – 3.0 × ULN	3.0 – 5.0 × ULN	> 5.0 × ULN
L15. T. bilirubin	1.1 – 1.4 × ULN	1.5 – 1.9 × ULN	2.0 – 3.0 × ULN	> 3.0 × ULN
L16. LDH	1.3 – 2.4 × ULN	2.5 – 5.0 × ULN	5.1 – 10 × ULN	> 10 × ULN
M. Urinalysis				
M1. Haematuria	Micro only	Gross, no clots	Clots, transfusion < 2 units	Transfusion required
M2. Proteinuria (per 24 h)	300 – 500 mg (tr/1+)	501 – 1999 mg (2+)	2 – 5.0 g (3+) nephrotic syndrome	5.0 g (4+) anasarca
M3. WBC in urine	NA	NA	Indicating acute interstitial nephritis	Associated with acute renal failure
M4. Uric acid crystals	Present without symptoms	NA	With stones or symptoms of stones (e.g., renal colic)	Causing renal outflow obstruction and hospitalization

\* In L11, 1.5 – 1.8 × ULN is changed to 1.4 – 1.8 × ULN.

\*\* In L14, 1.1 – 2.0 × ULN is changed to 1.1 – 1.5 × ULN.

\*\*\* In L3, L7 and L8, mg/dl is changed to mmol/l.

\*\*\*\* For CPK and Creatinine NCI CTC grading will be used. For CPK therefore the following gradings apply: Grade 1:  $> \text{ULN} - 2.5 \times \text{ULN}$ ; Grade 2:  $> 2.5 - 5.0 \times \text{ULN}$ ; Grade 3:  $> 5.0 - 10.0 \times \text{ULN}$ ; Grade 4:  $> 10.0 \times \text{ULN}$ ; For Creatinine the following gradings apply: Grade 1:  $> 1 - 1.5 \times \text{Baseline}$ ;  $> \text{ULN} - 1.5 \times \text{ULN}$ ; Grade 2:  $> 1.5 - 3.0 \times \text{Baseline}$ ;  $> 1.5 - 3.0 \times \text{ULN}$ ; Grade 3:  $> 3.0 \text{ baseline}$ ;  $> 3.0 - 6.0 \times \text{ULN}$ ; Grade 4:  $> 6.0 \times \text{ULN}$

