An important medical event that may not be immediately life-threatening or result in death or hospitalization, but based on medical judgment may jeopardize the subject and may require medical or surgical intervention to prevent any of the outcomes listed above (i.e., death of subject, life threatening, hospitalization, prolongation of hospitalization, congenital anomaly, or persistent or significant disability/incapacity). Additionally, any elective or spontaneous abortion or stillbirth is considered an important medical event. Examples of such events include allergic bronchospasm requiring intensive treatment in an emergency room or at home, blood dyscrasias or convulsions that do not result in inpatient hospitalization, or the development of drug dependency or drug abuse.

All AEs reported from the time of study drug administration until 30 days after discontinuation of study drug administration will be collected, whether solicited or spontaneously reported by the subject. In addition, SAEs and protocol-related nonserious AEs will be collected from the time the subject signs the study-specific informed consent.

AbbVie will be responsible for Suspected Unexpected Serious Adverse Reactions (SUSAR) reporting for the Investigational Medicinal Product (IMP) in accordance with global and local requirements.

AEs will be monitored throughout the study to identify any of special interest that may indicate a trend or risk to subjects.

Adverse Events of Special Interest

The following adverse events of special interest (AESI) will be monitored during the study:

- Serious infections
- Opportunistic infections
- Herpes zoster
- Tuberculosis
- Malignancy (all types)
- Gastrointestinal perforations
- Adjudicated cardiovascular events (e.g., major adverse cardiovascular event [MACE])
- Anemia
- Neutropenia

- Lymphopenia
- Increased serum creatinine and renal dysfunction
- Hepatic events and increased hepatic transaminases
- Elevated creatine phosphokinase
- Embolic and thrombotic events (non-cardiac, non-CNS)

Adverse Event Severity and Relationship to Study Drug

The investigator will rate the severity of each AE according to the Rheumatology Common Toxicity Criteria v.2.0. **If no grading criteria are provided for the reported event, then the event should be graded as follows:**

- Mild (Grade 1): Asymptomatic or mild symptoms; clinical or diagnostic observations only; intervention not indicated.

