### **9.3 Analysis of Laboratory Data**

Data collected from central and local laboratories, including additional laboratory testing due to an SAE, will be used in all analyses, except for Baseline, where SAE-related laboratory assessments on or before the first dose of study drug will be excluded.

Baseline is defined as the last available measurement before Study M16-063 study drug administration. The clinical laboratory tests defined in the protocol operations manual (e.g., hematology and clinical chemistry) will be summarized.

Mean change from baseline to each applicable post-baseline visit will be summarized for selected laboratory variables, with the number of observations, baseline mean, and visit mean, at each visit in Study M16-063 and Study M16-763 for each treatment group. An ANOVA model with only treatment as a factor, not controlling for baseline, will be used to test statistical significance for the mean change from baseline among different arms.

The baseline and post-baseline laboratory observations will be categorized as Grade 1, Grade 2, Grade 3, and Grade 4 according to OMERACT criteria (Rheumatology Common Toxicity Criteria v.2.0). For creatine phosphokinase and creatinine, NCI CTC criteria will be used.

For each laboratory variable, shift tables will be generated that cross tabulate the subjects as deemed appropriate by "as treated" treatment group:

- Category of the baseline value versus category of the final value.
- Category of the baseline value versus maximum category.
- Category of the baseline value versus minimum category.

Note that the minimum/maximum category is used, rather than the category of the minimum/maximum value. The two may be different due to variation in the reference range.

No statistical tests will be performed for this analysis.

Laboratory abnormalities will be evaluated based on Potentially Clinically Significant (PCS) criteria ([Appendix C](#)). For each laboratory PCS criterion, the number and percentage of subjects who have a laboratory value meeting the criteria will be summarized. Listings will be provided to summarize subject-level laboratory data for subjects meeting PCS criteria.

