## **Appendix C. Potentially Clinically Significant Criteria for Safety Endpoints**

The criteria for Potentially Clinically Important (PCS) laboratory findings are determined by OMERACT criteria in Table C-1, and the PCS criteria for vital sign findings are described in Table C-2.

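### The creatinine Grade 1 rule counts any rise above a single baseline and laboratory PCS has no minimum grade, so chance variation fills the creatinine PCS count and the 0-to-1 shift cell

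*SAP*

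**What the plan says.** SAP Section 9.3 grades laboratory values by the OMERACT criteria with one exception: "For creatine phosphokinase and creatinine, NCI CTC criteria will be used". The footnote to Table C-1 gives that scale, introduced by "For Creatinine the following gradings apply". Each of Grades 1 and 2 has two limbs separated by a semicolon:

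- Grade 1: above 1 and up to 1.5 × baseline; above ULN and up to 1.5 × ULN.
- Grade 2: above 1.5 and up to 3.0 × baseline; above 1.5 and up to 3.0 × ULN.

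Grade 3 also has a baseline limb (above 3.0 × baseline) and Grade 4 is by ULN only. The footnote does not say whether the limbs are alternatives or must both be met.

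Appendix C states that PCS "laboratory findings are determined by OMERACT criteria in Table C-1" and gives no minimum grade. Section 9.3 then says: "For each laboratory PCS criterion, the number and percentage of subjects who have a laboratory value meeting the criteria will be summarized". It asks for no confirmation or persistence. It also plans a shift table of "Category of the baseline value versus maximum category". Baseline is one measurement, the last before study drug in Study M16-063.

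Section 11.0 lists PCS for hematology and chemistry among the key interim safety outputs.

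**The concern.** A baseline value cannot exceed itself. A subject whose baseline creatinine is within the normal range therefore starts with no grade and moves to Grade 1 at the first later value that is higher by any amount, including one well inside the normal range. With no grade floor for PCS, that value also counts as a PCS finding and puts the subject in the PCS listing.

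The plan's other change-from-baseline criteria have a margin. Hemoglobin needs a fall of at least 1.0 g/dL (Table C-1, K1). Vital signs need changes of 10–20 mmHg, 15 bpm or more than 7% of weight (Table C-2). The creatinine row that the footnote replaces (L11) starts at 1.1 × ULN, and the CPK scale in the same footnote starts above ULN.

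At stake is how informative the creatinine PCS count, the PCS listing and the Grade 1 column of the shift table are. The PCS count is also an interim output.

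**Working it through.** The documents give no expected rate of creatinine Grade 1 or PCS, so there is no plan figure to reproduce. The check asks how often the rule is met with no drug effect.

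**Inputs from the documents**
- Rule: any post-baseline value above baseline is at least Grade 1 (Table C-1 footnote, limbs read as *or*).
- Scheduled extension visits with chemistry: 6, at Weeks 18, 24, 30, 36, 48 and 60 (protocol Appendix D).
- Expected completion: 20–60%, or 40 to 120 subjects (SAP Section 2.4). Both ends imply the same base: 40/0.20 = 120/0.60 = 200.

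**Assumptions, not in the documents**
- Within-subject CV of 4–10%.
- Mean creatinine 0.8 mg/dL, with between-subject SD of 0 or 0.15.
- ULN of 1.2 mg/dL.
- Reporting precision, serial correlation and the timing of dropout.

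**Which way to read the semicolon.** If both limbs had to be met, a value above 1.5 × baseline but below ULN would have no grade at all. *Or* is therefore the natural reading.

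**Reference case.** If the baseline and k later values are exchangeable without ties, the baseline is the highest of k + 1 values with probability 1/(k + 1). So P(at least one later value above baseline) = k/(k + 1).
- Six extension visits: 6/7 = 85.7% (simulation 85.6–85.8%).
- Adding the Week 12 value: 7/8 = 87.5%.
- Ten post-baseline values in all, counting further Study M16-063 visits (number assumed): 10/11 = 90.9%.

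**Attrition, extension visits only**
- Dropouts spread evenly over visits 1–5: their average is (1/2 + 2/3 + 3/4 + 4/5 + 5/6)/5 = 0.71. At 20% completion: 0.20 × 0.857 + 0.80 × 0.71 = 74%. At 60%: 0.60 × 0.857 + 0.40 × 0.71 = 80%.
- All dropouts leave after one visit: 0.20 × 0.857 + 0.80 × 0.5 = 57%, and 0.60 × 0.857 + 0.40 × 0.5 = 71%.

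**Precision and correlation, six attended visits (simulation)**

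| Setting | Share with any value above baseline |
|---|---|
| Reported to 0.01 mg/dL, CV 4–10% | 82–85% |
| Reported to 0.1 mg/dL, CV 4–10%, SD 0.15 | 42–69% |
| Reported to 0.1 mg/dL, CV 4–10%, every subject at 0.8 mg/dL | 33–70% |
| Serial correlation 0.3 to 0.8, CV 6%, to 0.01 mg/dL | 82% falling to 76% |

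The 33% end arises because 0.8 mg/dL is the centre of a rounding interval. Attrition combined with 0.1 mg/dL reporting would lower these shares further.

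**Comparison with the other limbs, six visits, CV 4–10%.** Exceeding 1.5 × baseline by chance: about 0–1.2%. Exceeding the assumed ULN: about 0–4.5%.

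**Effect on contrast.** At a 6/7 background, one arm can exceed another by at most 1 − 6/7 = 14 percentage points in an any-grade count.

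**The case against.** Three points on the other side have force.

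*The signal is not lost.* A reader might infer that the tables cannot show a renal effect. They can. Section 9.3 grades values 1 to 4, and only the 0-to-1 cell is inflated; Grade 2 and higher arises by chance in about 0–1.2% of subjects. The same section gives mean changes by visit and arm for selected variables, which do not depend on grading. This stands, and it limits the problem to the any-grade PCS count, the PCS listing and the Grade 1 cell.

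*The event of special interest is found another way.* Protocol Section 6.1 lists "Increased serum creatinine and renal dysfunction", and a reader might infer that the footnote distorts that category. SAP Section 9.2.6 and Appendix B identify the renal category by a narrow MedDRA query on reported events, and the Renal eCRF in protocol Table 3 has its own absolute creatinine threshold. Neither uses these grades. This stands too.

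*PCS may be meant by grade.* Section 9.3 counts subjects for each PCS criterion, which allows one row per grade. Then only the Grade 1 row would be uninformative. The text permits this but does not say it, so the any-grade reading remains open.

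A reader might also take 6/7 as the expected rate. It needs six attended visits, exchangeable values, no ties and no Study M16-063 values. The plan's own 20–60% completion sits badly with full attendance, although protocol Section 5.6 asks subjects who stop study drug to keep attending.

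**Conclusion.** Wrong as written, and minor. The footnote states a rule that, followed literally with the limbs joined by *or*, makes any value above one baseline measurement Grade 1. Appendix C then makes it PCS for want of a grade floor. With no drug effect the share flagged is about 57–91% with finely reported values, depending on attrition and on whether Study M16-063 visits count. It is about 33–70% over six attended visits if values are reported to 0.1 mg/dL. These ranges rest on assumed variability, precision and dropout timing.

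The excess is expected in every arm. It dilutes a difference in the creatinine PCS count, including at the interim analysis, and does not favour a group. Efficacy results are untouched.

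**What to change.** - **Table C-1 footnote.** For the PCS and shift tables, define creatinine Grade 1 as above ULN and up to 1.5 × ULN only. Keep the baseline limbs from Grade 2 up. State that the limbs combine as *or*, with the higher grade taken.
- **Appendix C.** Report creatinine PCS by grade, or as Grade 2 or higher and worse than baseline.

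A Grade 3 floor for every laboratory parameter should not be part of the change. It reaches well beyond creatinine, and it would drop a subject whose creatinine doubled but stayed within 3 × ULN from the PCS table.

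The cost is one footnote edit and one line of text, with no change to data collection. The downside is a small departure from the adopted NCI CTC Grade 1 wording: a rise of up to 1.5 × baseline that stays within the normal range would no longer carry a grade in these tables, though it would still contribute to any creatinine mean-change summary.

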**Table C-2. Criteria for Potentially Clinically Significant Vital Sign Values**

Vital Sign	Category	Criteria for Potential Clinically Significant Vital Signs
Systolic blood pressure	Low	Value $\leq$ 90 mmHg and/or decrease $\geq$ 20 mmHg from Baseline
	High	Value $\geq$ 160 mmHg and/or increase $\geq$ 20 mmHg from Baseline
Diastolic blood pressure	Low	Value $\leq$ 50 mmHg and/or decrease $\geq$ 10 mmHg from Baseline
	High	Value $\geq$ 100 mmHg and/or increase $\geq$ 10 mmHg from Baseline
Pulse	Low	Value $\leq$ 50 bpm and/or decrease $\geq$ 15 bpm from Baseline
	High	Value $\geq$ 120 bpm and/or increase $\geq$ 15 bpm from Baseline
Weight	High	> 7% increase from baseline
	Low	> 7% decrease from baseline
